5.5.6 Other recipients of adverse event reports and supplemental data  
Adverse events determined to require expedited reporting must also be reported by the institution, according to the local policy and procedures, to the Institutional Review Board responsible for oversight of the patient.

5.6 Duration of Intervention

Patients assigned to Arm B will receive up to 12 weeks of NRT. NRT will be dispensed in 4-week increments.

Patients assigned to Arm B will receive counseling for approximately 6 months.

Patients will receive protocol counseling and NRT (if randomized to Arm B) unless:

- Extraordinary Medical Circumstances: If at any time the constraints of this protocol are detrimental to the patient's health, protocol treatment should be discontinued. In this event submit forms according to the instructions in the EAQ171CD Forms Packet.
- Patient withdraws consent.

Rev. Add3

**5.7 Duration of Study and Follow-up**

Patients in this study may be followed for up to one year.

## 6. Measurement of Effect

### 6.1 Biochemical Samples

#### 6.1.1 Primary effectiveness outcome

The primary outcome is 7-day point-prevalence tobacco abstinence at 6-months follow-up, confirmed biochemically by saliva cotinine or expired air CO. Point-prevalence is biochemically verifiable and highly correlated with continuous and sustained abstinence.

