### 2.2 Primary Objective:

#### 2.2.1 Treatment effectiveness (Aim 1)

To compare the proportions of participants in the Enhanced Usual Care (EUC) and Virtual Tobacco Treatment (VIT) study arms with biochemically-verified 7-day point-prevalence abstinence from cigarettes at 6-months post enrollment.

We will define biochemically-verified 7-day point-prevalence abstinence at 6 month follow-up by:

- saliva cotinine (< 15 ng/ml), or
- expired air CO (< 10ppm)

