#### 5.3.1 Terminology

Counseling structure and content: The initial session will last approximately 40 minutes; follow-up sessions will last approximately 15 minutes.

All counseling sessions will be structured in a 5 As, patient-centered format and will include a variety of psycho-educational topics (see Table below).

Session #	Counseling Topics		Cessation Medication
1	Weekly	
 
• Smoking assessment
 
• Barriers to quitting and strategies to enhance readiness
 
• Medication education and assistance
 
	
 
• Introduction to NRT & use
 

2		
 
• Cancer related care and distress, care team communication
 
• Assess medication adherence and managing side effects
 
• Knowledge about quitting at the time of diagnosis
 
	
 
• NRT question/side effects
 

3		
 
• Coping with cravings and withdrawal
 
• Introduction to social support
 
• Introduction to mindfulness
 
	
 
• Assess NRT use & 2nd dose
 

4		
 
• Introduction to Stress management – deep breathing exercises
 
	
 
• Review 2nd dose/NRT fit
 

5	Bi-Weekly	
 
• Introduce beginning with appreciations
 
	
 
• Assess
 

Session #	Counseling Topics	Cessation Medication
Monthly	
 
• Values clarification exercise
 
• Smoke free home and car
 
• Nicotine and addiction
 
• Pleasurable behaviors
 
	adherence during treatment
	
 
• Smoking associated stigma and negative self-talk
 
• Stress Management 2 – battery exercise
 
• Weight gain concerns
 
• Review values clarification exercise
 
	
 
• Assess adherence during/post treatment
 

	
 
• Risk of other forms of tobacco
 
• Types of social support
 
• Stress management 3 – stress signs and coping
 
	
 
• Assess adherence during/post treatment
 

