#### 6.1.3 Definition of biochemically-confirmed quit

##### 6.1.3.1 **Saliva samples**

Saliva samples will be collected from all subjects who report being quit at 3- and/or 6-month follow-up who do not report concurrent NRT or e-cigarette use. Saliva samples will be tested for cotinine, which is a chemical the body makes when exposed to nicotine.

6.1.3.1.1 Saliva cotinine scores of < 15ng/ml will be considered biochemically-confirmed quit.

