**6.2.2.3 Smoking history**

Patients will be asked information about their smoking history (i.e., # of years smoked, daily smoking rate, 24-hour quit attempts, other tobacco/nicotine use, current and past use of tobacco treatments) using items adapted from the Cancer Patient Tobacco Use Questionnaire (C-TUQ), developed by the NCI-AACR Cancer Patient Tobacco Use Assessment Task Force designed to capture information about tobacco use for cancer patients and survivors. Nicotine dependence will be assessed using the 2-item Heaviness of Smoking Index from the Fagerstrom Test for Nicotine Dependence (FTND), which has predictive validity with the FTND.

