## 9. Statistical Considerations

### 9.1 Estimated Effect Size

Based on our current trial preliminary findings (Preliminary Studies) and previous trial with low SES smokers, we conservatively estimate 7-day point-prevalence tobacco abstinence at 6-month follow-up will be 15% for the standard care group and 32% for the intervention group. This estimate is based on our current trial, which has a higher intensity control group.

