### 9.2 Power calculation:

#### 9.2.1 Aim 1. Primary effectiveness outcome.

The study will have 80% power to detect a 17% difference in 7-day point-prevalence tobacco abstinence with a two-sided significance level of 0.01 with 280 participants.

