9.6 Plans for analyzing the primary objectives: treatment effectiveness (Aim 1)

The primary objective is to compare the proportions of participants in the study arms with 7-day point-prevalence abstinence from cigarettes at 6-months post enrollment. We will define 7-day point-prevalence by saliva cotinine (< 15 ng/ml) or expired air CO (<10 ppm). All participants who report being quit and no NRT or e-cigarette use will be requested to provide saliva samples, expired air CO will be measured in participants who report being quit and report concurrent NRT or e-cigarette use. If a participant is lost to follow-up or does not provide a saliva or CO sample, they will be considered a current smoker. The primary analysis will be performed from an intent-to-treat perspective. Chi-square tests will be used to compare the outcomes between treatment groups. Outcomes will be considered different with  $p<0.01$ .

As a randomized study, it is hoped that the two groups will be balanced between potential confounders. Appropriate comparisons between the groups will be performed (chi-squared tests, t-tests, etc.) to identify any potential confounders that were not balanced. If significant areas of imbalance are identified, logistic regression modelling will be performed to adjust for potential confounding.

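### The primary endpoint is abstinence from cigarettes in some sections and tobacco abstinence in others, and the assay routing sends cigarette quitters who use other non-combusted nicotine products to cotinine

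*Combined protocol and SAP*

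**What the plan says.** The primary objective in 2.2.1 is "biochemically-verified 7-day point-prevalence abstinence from cigarettes at 6-months post enrollment". The analysis plan in 9.6 agrees and compares "participants in the study arms with 7-day point-prevalence abstinence from cigarettes at 6-months post enrollment". Section 6.2.1.1 defines a current smoker by a cigarette in the past 7 days, and the self-report questions in 9.7 are also about cigarettes.

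Section 6.1.1 uses another term: "The primary outcome is 7-day point-prevalence tobacco abstinence at 6-months follow-up, confirmed biochemically by saliva cotinine or expired air CO". Section 6.1.2 does the same for the 3-month outcome, and the schedules in 7.5 and 11.3 list tobacco abstinence. The design rates in 9.1 are given as "7-day point-prevalence tobacco abstinence at 6-month follow-up will be 15% for the standard care group and 32% for the intervention group", and 9.2.1 claims "80% power to detect a 17% difference in 7-day point-prevalence tobacco abstinence with a two-sided significance level of 0.01 with 280 participants".

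On verification, saliva goes to self-reported quitters "who do not report concurrent NRT or e-cigarette use", with quit confirmed below 15 ng/ml. Self-reported quitters who do report NRT or e-cigarettes go to expired CO, with quit confirmed below 10 ppm. Sections 7.1 and 10 give the reason for the diversion, which is to prevent false positives, and set a last-week window. Section 6.1.3.1 says that cotinine is formed on exposure to nicotine. Other products are known to the plan: 6.2.2.3 collects "other tobacco/nicotine use, current and past use of tobacco treatments", but as a moderator and not as a routing variable.

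**The concern.** Cigarette abstinence and tobacco abstinence differ for anyone who has stopped cigarettes but uses another tobacco product. The routing matches neither definition for users of non-combusted products other than NRT and e-cigarettes. Two such patients with the same cigarette behaviour can receive opposite primary-outcome scores, depending on whether NRT or an e-cigarette was also used in the last week. The study supplies NRT to Arm B only, so the share sent to CO could differ by arm. The outcome also feeds the sustained-abstinence endpoint (verified at 3 and 6 months) and the incremental cost per quit. With two names in the text, the definition to be reported could be chosen after the data are seen.

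**Working it through.** **1. The plan's own figure.** Inputs from 9.1 and 9.2: 32% and 15%, two-sided alpha 0.01, power 80%, unpooled Z-test.

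n per arm = (2.576 + 0.842)² × (0.32×0.68 + 0.15×0.85) / 0.17² = 11.68 × 0.3451 / 0.0289 ≈ 139.5, so 140 per arm and 280 in total. Power at 140 is 0.8018, and the table gives 0.80184. The figure reproduces. The terminology does not affect this arithmetic, but it leaves open which event the 15% and 32% describe.

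**2. The terms side by side.**

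| Place | Term |
|---|---|
| 2.2.1, 9.6, 9.7, self-report in 6.2.1.1 | cigarettes |
| 6.1.1, 6.1.2, 9.1, 9.2.1, schedules in 7.5 and 11.3 | tobacco |

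**3. The routing applied.** Take a patient who has quit cigarettes and uses smokeless tobacco or a pouch.

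- *Neither NRT nor e-cigarette in the last week:* saliva. Cotinine reflects nicotine from any source, so the result is probably at or above 15 ng/ml and the patient is scored a smoker. This is wrong under 2.2.1 and 9.6.
- *NRT or e-cigarette as well:* CO (offered, in 7.1 and 10). The product is not burned, so the reading is probably below 10 ppm and the patient is scored quit. This is right for cigarettes and wrong for tobacco.
- *E-cigarette only:* CO with or without NRT, which is consistent with a cigarette endpoint.
- *Cigars or other combusted tobacco:* CO may itself be raised, so neither route clearly isolates cigarettes, and no rule is stated.

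**4. Size, on assumed inputs.** None of these shares is in the documents. Let s be the share of true cigarette quitters using such a product, and k the share of those users who also report NRT or e-cigarettes. Assume that CO reads below 10 ppm and cotinine at or above 15 ng/ml. A true cigarette quit rate p is then scored as p × [1 − s(1 − k)].

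*Equal true quit rates p0 in both arms.* The artefact is p0 × s × (k in VIT − k in EUC).
- Low end: 0.15 × 0.05 × (0.30 − 0.10) = 0.0015, or 0.15 points.
- High end: 0.32 × 0.10 × (0.50 − 0.10) = 0.0128, or 1.3 points.

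Both favour VIT, because k is assumed higher there.

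*Planned rates, taken for illustration as true cigarette abstinence, with k = 10% in EUC and 30% in VIT.* At s = 5%, EUC is 0.15 × (1 − 0.05×0.90) = 0.143 and VIT is 0.32 × (1 − 0.05×0.70) = 0.309. The difference is 16.6 points and power at 140 per arm is 0.79. At s = 2% the figures are 16.8 points and 0.80; at s = 10%, 16.1 points and 0.78.

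*A tobacco definition instead.* The difference becomes 17 × (1 − s): 16.7, 16.15 and 15.3 points at s = 2%, 5% and 10%, with power 0.79, 0.77 and 0.73.

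**5. Timing.** On the approximate schedule in 7.3, the third 4-week NRT fill is at week 9, so supply runs to about week 12. VIT 3-month follow-up starts at about week 10 and 6-month follow-up at about week 21. With a last-week window, study NRT can overlap the 3-month verification but has mostly ended by the primary time point.

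**The case against.** The strongest reply is that the endpoint is not ambiguous in operation. The objective, the analysis plan, the self-report definition and eligibility all concern cigarettes, and the scoring rule is the same wherever it appears. Reading tobacco for cigarettes would not alter the dataset produced. This stands: a reader might infer that the primary endpoint is undefined, and the documents do not support that. What remains is that the stated routing gives a wrong score under the plan's own operative definition.

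Three other stronger readings also fail.

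- *NRT alone decides the score.* The trigger is NRT or e-cigarettes, so e-cigarette users are handled consistently.
- *The endpoint is materially biased towards VIT.* Study NRT lasts up to 12 weeks. Section 6.5 expects quitline data on NRT dispensed to EUC patients, so NRT is not confined to one arm. The VIT session table includes "Risk of other forms of tobacco", but EUC patients are referred to quitline counselling whose content is not given, so no contrast in counselling on other tobacco can be asserted.
- *Several points of each arm's quit rate are at stake.* Multiplying 32% and 15% by an assumed share of other-product users would suggest this. But 9.1 draws partly on the preceding trial, whose 6-month rates 1.2.1 reports as cotinine-validated, so patients who fail cotinine would not be among those quitters. The product is also not a net difference between arms.

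A last objection is practical. CO must be done in person (10.2) with one device per site (10), and a missing sample counts as smoking, so more CO referrals could create new false smokers. This carries little weight, because most of these patients would fail cotinine and be scored smokers anyway.

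**Conclusion.** The concern holds in a limited form. Two terms are in use for the primary outcome, and cigarettes is the better supported. For cigarette quitters using a non-combusted nicotine product other than NRT or e-cigarettes, the routing probably gives a false smoker score, and it reverses if NRT or an e-cigarette is also reported. The protocol's own reason for diverting patients to CO applies equally to them.

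The effect is probably small: about 0.15 to 1.3 points between arms, against a planned 17. This rests on assumed shares (5-10% product use; 10% in EUC and 30-50% in VIT also reporting NRT or e-cigarettes), true quit rates of 15-32%, and assays behaving as expected. It is likely at the lower end at 6 months and possibly larger at 3 months. The sample size is not in error. The change should still be made, because this is the confirmatory endpoint and the correction is cheap.

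**What to change.** 1. Use *abstinence from cigarettes* in 6.1.1, 6.1.2, 7.5, 9.1, 9.2.1 and 11.3, and state that the 15% and 32% rates refer to it.
2. In 6.1.3, 7.1, 9.6, 9.7, 10 and 10.1.1, extend the CO trigger from NRT or e-cigarettes to any non-combusted nicotine product used in the last week (for example smokeless tobacco or pouches). First confirm that the other-tobacco item in the follow-up survey has a last-week look-back. The survey is not among the documents; 7.5 shows only that smoking history is collected at 3 and 6 months.
3. State how users of other combusted tobacco, such as cigars, are scored, since CO may be raised in them too.
4. Report all-tobacco abstinence, requiring no other tobacco by self-report, as a sensitivity analysis.

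The cost is an amendment of wording, one change to the existing EASEE-PRO trigger (plus a survey item change if the look-back is missing), and a few more in-person CO tests at sites that have one device each.

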#### 6.1.2 Secondary effectiveness outcome

7-day point-prevalence tobacco abstinence at 3-months follow-up is a secondary effectiveness outcome, confirmed biochemically by saliva cotinine or expired air CO. Point-prevalence is biochemically verifiable and highly correlated with continuous and sustained abstinence.

#### 6.1.3 Definition of biochemically-confirmed quit

##### 6.1.3.1 **Saliva samples**

Saliva samples will be collected from all subjects who report being quit at 3- and/or 6-month follow-up who do not report concurrent NRT or e-cigarette use. Saliva samples will be tested for cotinine, which is a chemical the body makes when exposed to nicotine.

6.1.3.1.1 Saliva cotinine scores of < 15ng/ml will be considered biochemically-confirmed quit.

##### 6.1.3.2 **Expired air CO samples**

Expired air CO breath tests will be offered to all subjects who report being quit at 3- and/or 6-month follow-up who also report concurrent NRT or e-cigarette use. The expired air tests will show carbon monoxide levels in the breath.

6.1.3.2.1 Expired air CO samples with a reading of < 10ppm^168 will be considered biochemically-confirmed quit.

### 6.2 Patient assessments

#### 6.2.1 Secondary smoking outcomes are commonly used in tobacco cessation trials and in our previous work. Reduction in smoking is important as most adult smokers reduce smoking as they try to quit; self-reported smoking status will additionally be used as it has been reported that deception of smoking status classification among cancer patients is low.

##### 6.2.1.1 Self-reported quit status

Patients will be asked on the 3- and 6-month follow-up surveys, how long it has been since they last smoked a cigarette, even one or two puffs. "Current smoker" will be defined as smoking a cigarette, even one or two puffs, in the past 7 days. (See Supplemental Appendices B: 3-

month Survey and C: 6-month Survey). This will be used to generate secondary outcomes of self-reported 7-day point prevalence abstinence, continuous and sustained abstinence (See Section [2.3](#) for definitions).

**6.2.1.2 Significant reduction in daily smoking**

Patients will be asked at baseline, 3-, and 6-month follow-ups, in the past 30 days, (1) on how many days they smoked cigarettes, and (2) how many cigarettes per day they typically smoked. “Significant reduction” will be defined as a > 50% reduction in cigarettes per day from baseline to 3- and 6-month follow-ups. (See Supplemental Appendix A: Baseline Survey)

**6.2.2 Exploratory objectives – Moderators and Mediators:** We will collect information on the following baseline factors and modifiable characteristics that may affect the association between treatment group and effectiveness outcomes. The following factors have been selected from the theoretical models, the Self-Regulation Model (SRM) and the Health Belief Model (HBM), that have informed this intervention, as well as based on our previous research.

**6.2.2.1 Sociodemographics**

Patients will be asked information about their sociodemographic characteristics (i.e., sex, age, marital status, race/ethnicity, education level, health insurance) at baseline. Financial burden will be assessed using 3 items from [name] national health insurance survey.

**6.2.2.2 Medical history**

**Alcohol use**

Patients will be asked about alcohol use using the Alcohol Use Disorders Identification Test (AUDIT-C), a three-item brief screening test for heavy drinking or alcohol dependence.

**6.2.2.3 Smoking history**

Patients will be asked information about their smoking history (i.e., # of years smoked, daily smoking rate, 24-hour quit attempts, other tobacco/nicotine use, current and past use of tobacco treatments) using items adapted from the Cancer Patient Tobacco Use Questionnaire (C-TUQ), developed by the NCI-AACR Cancer Patient Tobacco Use Assessment Task Force designed to capture information about tobacco use for cancer patients and survivors. Nicotine dependence will be assessed using the 2-item Heaviness of Smoking Index from the Fagerstrom Test for Nicotine Dependence (FTND), which has predictive validity with the FTND.

#### 6.2.2.4 **Quality of life and emotions**

Emotional distress will be assessed using the NCCN's one-item Distress Thermometer that asks the respondents to rate their current level of distress on a scale ranging from "0" (No distress) to "10" (Extreme distress).

Coping will be assessed using a 1-item, 10-point scale asking how the subject has been able to cope with the current stress in their life, ranging from "0" (Not at all able) to "10" (Very much able).

Anxiety will be assessed using the PROMIS Item Bank Emotional Distress-Anxiety-Short Form 4a which was developed for the general adult population and which evaluates anxiety symptoms (e.g., "My worries overwhelmed me") over the past 7 days on a 5-point Likert scale with raw scores ranging from 4-20.

Depression will be assessed using the PROMIS Item Bank Emotional Distress-Depression Short Form 4a which was developed for the general adult population and which evaluates depression symptoms (e.g., "I felt hopeless") over the past 7-days on a 5-point Likert scale with raw scores ranging from 4-20.

If a patient is determined as at acute risk, the study investigators will reach out to the patient's oncology team immediately to recommend a visit to the emergency room.

The tobacco counselors will be trained to assess suicidality and be supervised by licensed psychologists to assess the best real-time approach to the safety issues that may arise.

We will include a standard disclaimer at the end of each study survey that stipulates that survey responses are not reviewed in real time. We will also provide guidance for individuals who feel that they need additional psychosocial support and possibly mental care:

"We do not review these surveys in real time. Many individuals in a similar situation may feel distressed, and the study investigators encourage you to speak to your cancer care team to find out about local psychosocial support services. Your well-being is important to us. The American Psychosocial Oncology Society (APOS) helpline and chat services are available to anyone who may need psychosocial support for coping with cancer and its treatment ([name]). If you are feeling highly depressed or anxious, you may call and speak to a professional hotline counselor at [contact]."

#### 6.2.2.5 **Cancer beliefs**

Cancer stigma will be measured using the Internalized Stigma and Constrained Disclosure subscales of the Lung Cancer Stigma Inventory (LCSI). These subscales have

been modified in wording for use in the general cancer population. The LCSI has preliminary psychometric evidence demonstrating reliability and validity. Items assess to what degree the subject has experienced certain situations since their cancer diagnosis (i.e., “I have been careful who I’ve told about my cancer”), and are scored on a 5-point Likert scale ranging from “Not at all” to “Extremely”.

#### 6.2.2.6

##### **Smoking beliefs**

Quit-smoking medication beliefs will be assessed using a modified version of the Attitudes about Nicotine Replacement Therapy Scale (ANRT-12), which asks about the subjects’ thoughts on the benefits of using nicotine replacement therapy (i.e., “NRT is easy to use”) on a 5-point agreement scale ranging from “1” (Strongly disagree) to “5” (Strongly agree).

Self-efficacy to quit and importance of quitting will be assessed using two 1 item, 10-point measurements ranging from “0” (Not confident at all; or; Not important at all) to “10” (Very confident; or; Very important).

Perceived benefits of quitting smoking will be evaluated using 5 questions about the benefits of quitting for decreasing risk for second primary cancer or recurrence and increasing cancer treatment efficacy, scored on a scale from “0” (Not at all) to “10” (Very much) (i.e., how much does quitting smoking reduce your chances of developing your cancer again?).

Quit-smoking medication beliefs will be assessed using a modified version of the Attitudes about Nicotine Replacement Therapy Scale (ANRT-12), which asks about the subjects’ thoughts on the benefits of using nicotine replacement therapy (i.e., “NRT is easy to use”) on a 5-point agreement scale ranging from “1” (Strongly disagree) to “5” (Strongly agree).

Stigma will be assessed using a 6-item scale measuring stigma related to being a smoker, which has been modified from a previously used measuring smoking related stigma among smokers with comorbid behavioral health conditions. Items ask how strongly subjects agree or disagree with statements such as “I have avoided telling others that I am a smoker” or “I have worried that others will view me unfavorably because I am a smoker”.

